10.5.3.2 Clinical Laboratory Values

Biochemistry, hematology, and coagulation parameters will be presented using box plots by visits and by cohort and trial part. In addition, individual patient biochemistry, hematology, and coagulation parameters during the trial will be presented graphically using longitudinal plots. Urinalysis parameters will be summarized using descriptive statistics.

Laboratory values outside normal range will be flagged, and all laboratory values will be listed including CTCAE grading of abnormal values.

10.5.3.3 Other Safety Assessments

Change in vital signs from baseline to end of trial participation will be summarized by visit, cohort, and trial part. Normal and abnormal findings in physical examination and ECG measurements will be presented in shift tables by visit, cohort, and trial part.

ECOG PS, body weight, and ADA results will be listed.

10.5.4 Pharmacokinetic Endpoints and Analyses

The PK endpoints will be derived based on the concentration time curves of Sym015, and the first infusion of Sym015 in both parts of the trial. Refer to [Table 11](#).

Table 11 PK Endpoints Definitions and Derivations

Symbol	Definition and derivation
C_{trough}	Trough concentration (i.e., concentration of Sym015 measured pre-infusion)
AUC_{τ}	Area under the concentration-time curve in a dosing interval (i.e., from time zero (end of infusion) up to 336 hours or 504 hours depending on regimes). AUC_{τ} will be calculated using the linear trapezoidal method and interpolated in case of measurements after 336/504 hours, or extrapolated using terminal rate constant and the last quantifiable concentration, C_z
C_z	Last quantifiable concentration. C_z is not an endpoint, but is used for derivation of endpoints
$AUC_{\text{norm, } \tau}$	Dose normalized area under the concentration-time curve in a dosing interval, calculated as AUC_{τ} divided by the dose infused
C_{max}	Maximum concentration
T_{max}	Time to reach maximum concentration
λ_z	Terminal rate constant (negative of the slope of an ln-linear regression of the un-weighted data considering the terminal phase of the concentration-time curve \geq limit of quantification. λ_z is not an endpoint, but is used for derivation of endpoints
$T_{1/2}$	Terminal elimination half-life, calculated as $\ln(2)/\lambda_z$
CL	Clearance (Dose/ AUC_{τ})
V_z	Volume of distribution during the terminal phase (CL/λ_z)

C_{max} , C_{trough} and T_{max} will be derived from observed data while AUC_{τ} , $AUC_{\text{norm, } \tau}$, CL, V_z , and $T_{1/2}$ will be estimated using non-compartmental methods and actual time points.

Individual curves of serum concentration versus time after the first dosing of Sym015 will be presented on log- and linear scale for all patients in the FAS. Furthermore, trough serum concentrations for the period from first dose to end of treatment will be presented on linear scale individual plots. In addition, mean concentration time curves will be presented on linear scale using nominal time point by cohort and trial part. All PK endpoints will be listed and summarized by cohort and trial part.

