3.2.3 Summary of Non-Clinical Findings

Sym015 demonstrates potent antitumor activity in a number of MET-dependent cell line and patient-derived xenograft (PDX) tumor models, including esophagogastric and NSCLC models. Response to Sym015 was observed in models with *MET*-amplification, *MET*^{Ex14Del}, and autocrine HGF-expression. Sym015 also retains full efficacy in *MET*-amplified models in human HGF transgenic mice. Sym015 is in many cases superior to a LY2875358 (emibetuzumab) analogue and is also active in tumor models that escape treatment with this antibody. Based on the preclinical models, *KRAS* mutation appears to predict resistance to Sym015 treatment (25,26).

In vivo safety and pharmacokinetics (PK) of Sym015 were evaluated in non-human primates. MET is evolutionarily conserved between cynomolgus monkeys and humans and Sym015 recognizes both human and cynomolgus MET with the same, high affinity. Thus, the cynomolgus monkey is considered a pharmacologically relevant model in which to study toxicity and PK.

In the pivotal repeat-dose toxicity study, the toxicity of Sym015 was determined following weekly IV infusions (30 minutes infusion time) at 15 mg/kg, 50 mg/kg, or 100 mg/kg to cynomolgus monkeys for 4 weeks followed by a 6-week treatment-free period in the high dose group.

No unscheduled deaths occurred during the course of the study. Sym015 did not exert effects on cardiovascular functions and was overall well tolerated in the monkeys. However, soft, liquid, or loose feces were observed in treated animals, with a higher incidence in high dose males. At the end of the recovery period, there was no evidence of delayed onset toxicity in previously treated animals.

No *in vivo* agonistic activity of Sym015 was observed as judged by Ki67 expression (proliferation marker) in liver, kidney, duodenum, and heart at study termination. Toxicokinetic profiles showed that all treated animals were exposed to Sym015 throughout the entire duration

of the study. Target engagement, documented by reduced MET expression in tissues, was observed for all dose levels tested.

In the initial elimination phase, the serum half-life ($T_{1/2}$) of Sym015 after a single dose of 15 mg/kg ranged from 8-23 days, while in the terminal elimination phase the $T_{1/2}$ ranged from 5-8 days. Upon repeat, once-weekly dosing of Sym015 at 15 mg/kg, 50 mg/kg, or 100 mg/kg produced a 2-fold accumulation of Sym015 over a period of four weeks.

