3.4.2 Rationale for Recommended Phase 2 Dose

As of Amendment 4, following review of available safety (refer to Section 3.2.4.1) and PK data, the decision has been made to choose the following as the recommended Phase 2 dose (RP2D) on a Q2W schedule of Sym015 (referenced as the Q2W RP2D):

- Loading dose of 18 mg/kg infused over 1.5 hours on Cycle 1/Day 1 (C1/D1)
- Followed by Q2W maintenance doses of 12 mg/kg infused over 1 hour beginning on Cycle 1/Day 15 (C1/D15)

The rational for this choice is based upon preliminary PK data from the initial 6 mg/kg Q2W (N=3, 2-3 cycles) and 12 mg/kg Q2W (N=3, up to Cycle 2/Day 1) cohorts treated in the dose-escalation phase of this trial. These data were used to establish a population PK model.

The summary PK parameters for these data, based on non-compartmental analysis, are listed in [Table 1](#).

Table 1 Preliminary Sym015 Geometric Mean PK Parameters

Dose Q2W	N	AUC _{0-336h} 1 st dose (h x µg/mL)	C _{max} 1 st dose (µg/mL)	C _{trough} 2 nd dose (µg/mL)	C _{max} 3 rd dose (µg/mL)	t _½ 1 st dose (h)
6 mg/kg	3	19400	146	35.9	196	158
12 mg/kg	3	40000	294	119	396	213 (n=1)

Abbreviations: AUC, area under the concentration-time curve in a dosing interval; C_{max}, maximum concentration; C_{trough}, trough concentration; h, hour; N, number of patients; Q2W, dosing every second week; t_½, elimination half-life

The model was used to simulate average and 90% confidence intervals for Sym015 PK profiles for the 18+12 mg/kg Q2W regimen, and demonstrated that pre-dose serum concentrations, C_{trough}, are likely to be above 100 µg/mL for the vast majority of patients for all dose administrations. The serum concentration of 100 µg/mL has been defined as an approximate threshold for clinical efficacy. This has been deduced from the 750 mg Q2W dose regimen of another anti-MET monoclonal antibody, emibetuzumab, which has shown signs of efficacy in patients with *MET*-amplified tumors ([23,28](#)). It is assumed that similar serum concentrations of Sym015 and emibetuzumab will result in similar clinical efficacy because similar potencies between the two compounds have been observed in preclinical *in vitro* and *in vivo* studies (refer to Investigator's Brochure). *In vivo* studies also support that efficacy can be expected at concentrations above 100 µg/mL for both compounds.

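### Table 11 computes CL as Dose/AUCtau from first-infusion data, which overstates clearance and the Vz built on it (minor; a formula or label correction)

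*Protocol*

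**What the plan says.** Section 10.5.4 states that the PK endpoints are "derived based on the concentration time curves of Sym015, and the first infusion of Sym015 in both parts of the trial". Table 11 in that section then gives the formulas:

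- AUCtau is the area from the end of infusion to the end of the dosing interval, which is 336 h for the two-weekly schedule. If samples stop early, it is completed by extrapolation: "or extrapolated using terminal rate constant and the last quantifiable concentration".
- The CL row begins "Clearance (Dose" and divides by AUCtau.
- The Vz row begins "Volume of distribution during the terminal phase (CL" and divides by lambda_z.
- No area to infinity is defined anywhere in the table.

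Table 9 (Section 8.4) places the extended sampling after the Cycle 1 Day 1 infusion. Later infusions have only a pre-infusion and an end-of-infusion sample.

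**The concern.** Dose divided by the area over one dosing interval is clearance only when the drug is at steady state, because only then does one interval hold the same area as a single dose followed to infinity. After a first dose, the area beyond the interval is still to come. Leaving it out makes the denominator too small, so CL is too high. Vz is CL divided by lambda_z and is too high by the same factor.

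The half-lives in Table 1 (158 h and 213 h) are long relative to a 336 h interval, so the omitted area need not be small. Characterising the PK profile is a secondary objective in both parts (Sections 4.1.2 and 4.2.2), and Section 10.5.4 has every PK endpoint listed and summarised by cohort and part. Figures labelled as clearance and volume would therefore be reported that are not those quantities, with an error that grows with the patient's half-life.

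**Working it through.** **Inputs** (Protocol Section 3.4.2, Table 1; geometric means, N=3 per dose)

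- 6 mg/kg: first-dose AUC0-336 19,400 h·µg/mL; Cmax 146 µg/mL after dose 1 and 196 after dose 3; half-life 158 h.
- 12 mg/kg: first-dose AUC0-336 40,000 h·µg/mL; Cmax 294 after dose 1 and 396 after dose 3; half-life 213 h, from one patient.

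The protocol prints no CL, Vz or AUC0-inf, so there is no stated figure to reproduce.

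**1. The identity.** Under linear kinetics, CL = Dose/AUC0-inf after a single dose and CL = Dose/AUCtau at steady state. Hence first-dose Dose/AUCtau = CL × (AUC0-inf/AUCtau). A one-compartment check with half-life 158 h and true CL 0.238 mL/h/kg gives first-dose Dose/AUCtau = 0.309 (ratio 1.297) and steady-state Dose/AUCtau = 0.238.

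**2. Table 11 applied to Table 1.** lambda_z = ln 2/half-life.

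- 6 mg/kg: CL = 6,000/19,400 = 0.3093 mL/h/kg; lambda_z = 0.004387/h; Vz = 0.3093/0.004387 = 70.5 mL/kg.
- 12 mg/kg: CL = 12,000/40,000 = 0.300 mL/h/kg; lambda_z = 0.003254/h; Vz = 0.300/0.003254 = 92.2 mL/kg.

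**3. Is there area beyond 336 h?** Yes. Cmax rises by dose 3 by a factor of 196/146 = 1.34 and 396/294 = 1.35, so drug is carried over. The direction of the bias does not depend on a model.

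**4. How large can it be?** Suppose the decline is a sum of exponentials and the Table 1 half-life is the slowest. A term with rate k has the share exp(-336k) of its area beyond 336 h, and k is never below lambda_z. The share of AUC0-inf beyond 336 h is then at most e = 2^(-336/half-life), and the overstatement of CL is at most 1/(1-e) - 1.

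| Half-life | e | 1/(1-e) | Overstatement, at most | CL, at least | Vz, at least |
|---|---|---|---|---|---|
| 158 h | 0.229 | 1.297 | 29.7% | 0.3093/1.297 = 0.238 mL/h/kg | 70.5/1.297 = 54.4 mL/kg |
| 213 h | 0.335 | 1.504 | 50.4% | 0.300/1.504 = 0.199 mL/h/kg | 92.2/1.504 = 61.3 mL/kg |

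**5. Ceiling, not estimate.** The bound is reached only if the curve is a single exponential. Run from the Table 1 Cmax, a single exponential would give AUC0-336 = (146/0.004387) × 0.771 = about 25,660 against 19,400 (+32%) at 6 mg/kg. At 12 mg/kg it would give (294/0.003254) × 0.665 = about 60,070 against 40,000 (+50%). Under multi-exponential decline the profile therefore falls faster early on, and the late share is below the ceiling.

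**6. Start of the area.** Counting from the end of infusion omits roughly 146 × 1/2 = 73 h·µg/mL at 6 mg/kg, or 73/19,400 = 0.4%, which is negligible.

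**The case against.** **The extrapolation might supply the missing tail.** It does not. In Table 11 it belongs to the definition of AUCtau and completes the interval when samples end before 336 h.

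**AUCtau might be meant at steady state.** Table 11 does not itself say first-dose clearance; that follows from joining its lead sentence, its formulas and Table 9. But Table 9 leaves no later profile from which a steady-state AUCtau could be computed.

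**The formula is printed, and nothing is tested.** This stands as a limit on importance. A reader can see which area is used, no comparison of CL is planned, and Section 10.1 rules out formal hypothesis testing. The RP2D rests on simulated troughs from a model ("These data were used to establish a population PK model"), not on CL.

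Some stronger readings are tempting, but the documents do not support them:

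- *A bias above the ceilings.* Back-calculating the 336 h concentration from the Table 1 troughs or Cmax rises gives overstatements of 34-48% at 6 mg/kg and 47-69% at 12 mg/kg. Under multi-exponential decline those concentrations need an AUC0-336 that is 16-86% above the one Table 1 reports. A curve whose decline only speeds up does not rescue them: joining Cmax to the lowest of these concentrations log-linearly already needs at least (146 - 29.2)/ln(146/29.2) × 336 = 24,384 against 19,400, and (294 - 76.4)/ln(294/76.4) × 336 = 54,255 against 40,000.
- *Clearance falling with dose.* The lower limits of 0.238 and 0.199 are bounds, not estimates, and the second uses one patient's half-life.
- *Redundancy as proof.* Table 11 also lists "Dose normalized area under the concentration-time curve in a dosing interval, calculated as" AUCtau over dose, which is the reciprocal of CL as printed. Dose/AUC is always the reciprocal of dose-normalised AUC, so this shows no error.
- *A problem special to the NSCLC cohorts.* Their late samples (48 h, Day 8, before the Day 15 infusion) are the same as in the other cohorts.

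**Conclusion.** The formula is wrong as written for the data it will be applied to, and the point is minor. CL and Vz will be overstated by AUC0-inf/AUCtau. The direction is firm; the size is not. Assuming linear kinetics and multi-exponential decline with the Table 1 half-lives, the overstatement is at most about 30% at 158 h and 50% at 213 h, equivalent to at most about 23% and 34% of AUC0-inf lying beyond 336 h.

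These ceilings rest on three patients per dose and, at 12 mg/kg, on one half-life. Table 1 has nothing at 18 mg/kg, the dose of the first infusion in Part 2. The shape of the decline after 336 h is also unknown. In monkeys the initial-phase half-life "of Sym015 after a single dose of 15 mg/kg ranged from 8-23 days, while in the terminal elimination phase the" half-life was 5-8 days. If decline in patients also speeds up, the tail is smaller than the first-interval slope implies and the multi-exponential bound no longer strictly applies; whether that pattern carries over is not known.

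A reader might infer that the dose selection or the efficacy results are compromised. They are not: the primary endpoints, the RP2D, T1/2, Cmax, Ctrough and AUCtau do not use these two formulas.

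**What to change.** Correct Table 11 as follows.

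- Where the profile supports it, define first-dose CL = Dose/AUC0-inf, with AUC0-inf = AUC0-tlast + Cz/lambda_z, and derive Vz from that CL. Report the percentage of AUC0-inf that is extrapolated for each profile, and flag profiles where it is large.
- Where extrapolation is unreliable, in any cohort, take CL and volume from the population PK model. Alternatively, relabel Dose/AUCtau so that it is not called clearance, and drop the Vz built on it.

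The cost is a formula or label change in Table 11 and the PK programs, plus one reported column. Cz and lambda_z are already derived and no new samples are needed. The population PK option requires the existing model to be updated with Part 2 data.

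The downside is that AUC0-inf is itself uncertain when the extrapolated share is large, and CL would be understated if decline speeds up after 336 h. Relabelling avoids that risk but yields no clearance estimate.

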--	---

	
EOC2 (i.e., coinciding with time of first response assessment) or upon PD, whichever occurs first.
 
Additional Assessments
 
• PK sampling with extended PK-profiling after the first infusion• Anti-drug antibody (ADA) testing• Part 1 only: Skin biopsy for biomarker analysis at screening, at the EOC2 or upon PD, whichever comes first• Blood sample for genomic/biomarker analyses at screening, at the EOC2 or upon PD, whichever comes first, and at EOT
Statistical Methods and Sample Size Calculation	
The primary endpoint of Part 1 of the trial is the occurrence of DLTs measured during Cycle 1 of Sym015 administration. The number of enrolled patients will depend on the extent of observed DLTs independently in each cohort. Based on a 3+3 design, it is planned to enroll between 12 and 15 patients during dose-escalation.
 
All DLT events will be listed by dose cohort and patient. A summary table of DLTs by System Organ Class (SOC) and Preferred Term will be presented for each dose cohort, if applicable. The summaries will include number of DLTs and number and percentages of patients experiencing a DLT.
 
The MTD is defined as the highest dose with a maximum of 1 out of 6 patients experiencing a DLT. The MTD may or may not be found within the dose levels tested. Based on an overall evaluation of the dose-escalation part, the Q2W RP2D and highest safe dose tested will be selected.
 
In Part 2 of the trial, the primary endpoint is documented, confirmed OR, assessed by RECIST v1.1 at any time during trial participation by Investigator assessment. It is planned to include approximately 25 patients with advanced solid tumor malignancies, documented and confirmed as MET-amplified in the Basket Cohort, 20 patients in the NSCLC MET-Amplified Cohort, and 6-12 patients in the NSCLC MET^{Ex14Del} Cohort, for a total of approximately 51-57 patients in Part 2. The expected (target) range of OR in any of the three cohorts is in the range of 20%-50%, depending on histology, previous therapies, and other prognostic factors defining the enrolled patient population.
 
Number and percentages of patients with documented OR will be presented including corresponding 90% exact Confidence Intervals (CI).

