7.1.3 Administration of Sym015

7.1.3.1 Treatment Schedule

All patients will be administered IV infusions of Sym015, dosed according to body weight, through a peripheral line or indwelling catheter, and with the use of an infusion pump and an inline filter. Sym015 will be administered Q2W (Day 1 and Day 15 of each 28-day cycle [± 2 days]).

For all Sym015 infusions, a complete dosing history will be recorded, i.e.,:

- Total dose and volume administered
- Start and stop time of infusion
- Infusion interruption or termination and reason for such actions

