8.4 Pharmacokinetic Assessments

PK samples will be taken according to the schedules shown in [Table 9](#).

Analysis of PK will be performed at a central laboratory. A detailed laboratory manual specifying sample collection, handling, storage, and shipment will be provided to the trial sites.

In the event that a collected serum sample is inadequate or insufficient for PK analysis, the analysis of PK can be done using an anti-drug antibody (ADA) serum sample from the same time point, if available.

Note: Comprehensive collection of clinical samples is critical to the conduct of this study. In situations where collection of EOI + 8h samples is logically difficult due to clinic staff availability, the observation period may be shortened and an "end of day" sample may be obtained at the latest practical time. Such an option (if to be routinely employed) is available only after previous discussion with and approval by the Sponsor.

Table 9 Schedule of Pharmacokinetic Assessments

		Cycle 1			Cycles Thereafter		EOT	IM FUP
Sampling Time	Window	D1-D3	D8	D15	D1	D15		
Part 1 / Part 2 Basket Cohort								
Prior to SOI	- 4 h	X		X ¹	X ¹	X ¹		
EOI	+ 10 min	X		X ¹	X ¹	X ¹		
EOI + 1 h	±15 min	X						
EOI + 2 h	±30 min	X						
EOI + 4 h	±30 min	X						
EOI + 8 h	±90 min	X						
EOI + 24 h	±6 h	X						
EOI + 48 h	±12 h	X						
During Visit	NA		X				X	X
Part 2 NSCLC Cohorts (effective with protocol v8.0; December 2018)								
Prior to SOI	- 4 h	X		X ¹	X ¹	X ¹		
EOI	+ 10 min	X		X ¹	X ¹	X ¹		
EOI + 4 h	±30 min	X						
EOI + 48 h	±12 h	X						
During Visit	NA		X				X	X

Abbreviations (in alphabetical order): D, day; EOI, End of Infusion, EOT, End of Treatment Visit; NA, Not Applicable; h, hour; min, minutes; 1M FUP, 1-Month Follow-up Visit; SOI, Start of Infusion

1) If Sym015 is paused, only one PK sample should be taken during the visit

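### Terminal half-life and Vz are tied to a 14-day first-dose profile spanning only about 1.6 to 2.1 half-lives, so in Part 2 they may be imprecise, available only in a subset, or not terminal

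*Protocol*

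**What the plan says.** Section 10.5.4 states that the PK endpoints are "derived based on the concentration time curves of Sym015, and the first infusion of Sym015 in both parts of the trial" and that T1/2, CL and Vz come from non-compartmental methods. Table 11 gives T1/2 as "Terminal elimination half-life, calculated as" ln(2)/λz, where λz is the log-linear slope of the terminal phase. Vz is the "Volume of distribution during the terminal phase", CL/λz, with CL = Dose/AUCτ.

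The Synopsis plans "PK sampling with extended PK-profiling after the first infusion". In Table 9 (Section 8.4), later infusions have only pre-infusion and end-of-infusion (EOI) samples, plus single samples at the End of Treatment (EOT) and 1-Month Follow-up (1M FUP) visits. Dosing is on "Day 1 and Day 15 of each 28-day cycle" (Section 7.1.3.1), so the first-dose profile ends at about 336 h. From 48 h on, it consists of EOI + 48 h, Day 8 and Day 15 pre-dose. This holds for Part 1 and the Basket Cohort and for the schedule headed "Part 2 NSCLC Cohorts (effective with protocol v8.0; December 2018").

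Section 3.4.2, Table 1 reports a first-dose half-life of 158 h at 6 mg/kg (N=3, no reduced number flagged) and 213 h at 12 mg/kg (n=1 of 3). AUC over 0–336 h is given with N=3 at both doses. Of the preliminary data the section adds: "These data were used to establish a population PK model". Part 2 begins with 18 mg/kg.

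Section 3.2.3 describes two phases in monkeys at 15 mg/kg: the initial half-life "ranged from 8-23 days, while in the terminal elimination phase" it was 5–8 days.

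**The concern.** A terminal slope needs a profile long enough to reach the terminal phase and to measure the decline within it. Here the next dose fixes the length, and the sponsor's first attempt at 12 mg/kg gave a half-life for one patient in three. Part 2 starts above both doses in Table 1. If the half-life can be estimated only where decline is fast enough to see in 14 days, the summary describes a selected subset. If the slope over that window depends on concentration, it is not the quantity its label claims. PK is a secondary objective in both parts (Sections 4.1.2 and 4.2.2), and these values would be read as descriptors of the antibody.

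**Working it through.** **1. Do Table 1's half-lives fit a 14-day window?** Two-point check: t½ = ln 2 × 336 / ln(Cmax/C336). The column for the second-dose trough is ambiguous, so both readings are used: the trough before dose 2, or the trough after dose 2 (solve x + x² = Ctrough/Cmax, with x = C336/Cmax).

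| Dose | Cmax | Ctrough | t½, before dose 2 | t½, after dose 2 | Table 1 |
|---|---|---|---|---|---|
| 6 mg/kg | 146 | 35.9 | 166 h | 147 h | 158 h |
| 12 mg/kg | 294 | 119 | 257 h | 198 h | 213 h |

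Both stated values are plausible.

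**2. Window in half-lives.**
- Whole profile: 336/158 = 2.13; 336/213 = 1.58.
- From 48 h: 288/158 = 1.82; 288/213 = 1.35.

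**3. Does the decline depend on dose?** From 6 to 12 mg/kg, Cmax rises 294/146 = 2.01-fold and AUC 40000/19400 = 2.06-fold, but trough rises 119/35.9 = 3.3-fold. The two-point half-lives (147–166 h against 198–257 h) do not overlap. This comes from the cohort means, so it does not rest on the single 213 h value. It suggests slower decline at higher concentration, the same direction as the monkey phases, but with three patients per dose.

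**4. Is 213 h typical of its cohort?** Reading the 119 as the trough after dose 2, C336 = 119/(1 + 0.335) = 89, where 0.335 is the fraction left at 336 h. A pure 213 h decline ending at 89 starts at 89/0.335 = 266 and encloses (266 − 89)/(ln 2/213) ≈ 54,000 h·µg/mL. Table 1 gives 40,000. At 6 mg/kg the same check gives about 22,400 against 19,400, a smaller gap. The one value reported at 12 mg/kg may therefore be a selectively short one. These are means of three, so this is only a hint.

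**5. Precision with three late samples.** Times 48, 168 and 336 h have mean 184, so Sxx = 136² + 16² + 152² = 41,856 and √Sxx = 204.6. At 213 h, λ = 0.00325 per h. With residual error on the log scale of 0.10, 0.15 or 0.20 (assumed; the protocol gives none), CV(λz) = error/(204.6 × 0.00325) = 15%, 22.5% or 30% per patient. A missed sample leaves two points.

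**6. Vz has a second problem.** Dose/AUCτ equals clearance only at steady state. After a first dose it overstates CL, and so Vz, by the factor 1 + (C336/λz)/AUC336:
- 6 mg/kg, C336 29.2–35.9: 1.34–1.42.
- 12 mg/kg, C336 89–119: 1.68–1.91.

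**7. Data already collected.** The 1M FUP sample is 30–37 days after the last dose: 720/213 = 3.4 to 888/158 = 5.6 half-lives. Section 10.5.4 assigns it to no half-life derivation.

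**The case against.** The strongest reply is that nothing in the protocol places the human terminal phase beyond Day 14. Table 1 is preliminary and gives no reason for n=1. The 6 mg/kg cohort, on the same late sampling times, shows no reduced number, and its 158 h (6.6 days) lies inside the monkey terminal range. One patient in three says little: the exact 90% interval is 2% to 86%. Section 10.5.4 does not say that only the first infusion may be used. The endpoints are descriptive, and Section 10.1 leaves analysis details to the SAP.

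Much of this stands. A reader might infer that T1/2 and Vz will be missing or will describe the wrong phase; the documents support only that they may. Three further inferences also fail:
- Reading 213 h against 158 h as a 35% phase error compares one patient with a mean of three at another dose.
- A several-fold error taken from the monkey ranges sets opposite extremes against each other and crosses species; the ranges meet at 8 days.
- The v8.0 schedule did not thin late sampling. It dropped EOI + 1, 2, 8 and 24 h and kept every time from 48 h on.

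The effect on AUC extrapolation is also minor, because an early Day 15 visit leaves at most about two days to fill.

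What the reply does not answer is that the protocol itself fixes the method, offers no other full profile for it, and labels the result terminal.

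**Conclusion.** The point holds as a risk. The profile assigned to T1/2 and Vz spans about 1.6–2.1 half-lives on the protocol's own figures (1.35–1.8 from 48 h), and a half-life was reported for 1 of 3 patients at 12 mg/kg. At the 18 mg/kg first dose of Part 2, the estimates may be imprecise (individual CV about 15–30%, under the assumed error and a 213 h half-life), limited to a selected subset, or taken from a slope that is not terminal. This rests on geometric means of three patients per dose, one half-life from a single patient, and an ambiguous trough label, hence the ranges. The first-dose clearance formula is a separate defect: it would inflate Vz by 34–91% on Table 1 figures even with a correct λz. The primary endpoints are unaffected.

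**What to change.** In Section 10.5.4 and Table 11, estimate T1/2 and Vz from the existing population PK model, updated with all Table 9 samples: the first profile, pre-dose and EOI samples at later infusions, and the EOT and 1M FUP samples. If elimination proves concentration-dependent, there is no single half-life, so state the concentration range to which the reported value applies.

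If the first-dose non-compartmental slope is kept, report it as an apparent half-life over 48–336 h, give the number of patients in whom it could be estimated, and do not derive Vz from it. Correct the use of Dose/AUCτ as first-dose clearance separately, since a better λz alone would leave Vz wrong.

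The cost is one modelling step in place of a direct calculation, with a model so far built on six patients at 6 and 12 mg/kg. No new samples are needed.
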